
Visit 12—follow-up fMRI testing (for the fMRI group): Follow-up fMRI will be performed on the subjects who had baseline fMRIs performed. These will be performed in the same fashion as described in Visit #3. In addition, patients may have urine and vaginal swab samples collected and stored for possible future analysis (For example, urine may be analyzed for biomarkers).

Final visit 11 (for those who did not undergo fMRIs) and Final visit 13 (for those who did undergo fMRI): The final study visit will be scheduled at the end of the hypnotherapy or medication counseling sessions, approximately 8-12 weeks after study entry. Those who are in the subgroup who have undergone prior fMRI testing will have it performed at this session. At the final study visit, subjects will 1) be administered the OABq-SF, ISI, the PPBC, CRADI-8, IBS Module and IC questionnaires, PISQ-12 and answer the question regarding

how well the therapy met their expectations for treatment. Their compliance with medications or home practice of hypnotherapy will be documented 2) They will return their follow-up voiding diary 3) receive patient incentives for the time and inconvenience they have experienced from study participation. In addition, patients may have urine and vaginal swab samples collected and stored for possible future analysis (For example, urine may be analyzed for biomarkers).

Length of visits: Each hypnotherapy session will last approximately 60 minutes, each pharmacotherapy visit will take approximately 20-60 minutes, and each Brain fMRI visit will last approximately 60-120 minutes. The 6 and 12 month visits may be conducted via phone or mail, if the subject desires, in order to decrease subject inconvenience.

B. NORMATIVE CONTROLS PARTICIPATING IN ONLY THE FMRI STUDY:

In addition to the UUI study subjects described previously, we will also enroll a group of women without UUI and OAB symptoms (and with OAB Awareness Tool screening questionnaire scores < 8). This normative group (approximately 30-35 subjects) will keep voiding diaries, answer questionnaires, and undergo urine pregnancy and dipstick testing and cystometric testing and receive prophylactic antibiotics (as described previously) followed by performance of a Brain MRI in order to compare baseline fMRIs in women with and without UUI.

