Screening: FMRI portion of the study explained to subject, including the cystometry and fMRI procedures. Subject administered OAB Awareness tool and fMRI eligibility assessed. Subject given voiding diary instructions. Subject given copy of consent and either has visit scheduled to sign consent after subject has time to consider whether she wants to participate in the study. If subject states she is certain that she wants to participate, she has the option of signing the consent at this time. If the consent is signed, then the subject is administered the medical history and demographic forms. If subject states at this visit that she would like to participate in the study, appointments are scheduled for the cystometry and fMRI and arrangements are made for the patient to receive prophylactic antibiotics prior to the bladder catheterizations. If patient is uncertain whether she wants to participate, the research coordinator's contact information is given to the subject.

Visit 1: Subjects return for the visit with the voiding diary and study eligibility is re-confirmed. The consent is signed, if this has not happened previously. The medical history and demographics forms are administered. POP-Q exam is performed if it has not been performed in the last year. Cystometry is explained to the subject once more. Urine pregnancy test is performed (if patient is premenopausal and has not had a hysterectomy or permanent sterilization procedure) and urine screen for UTI performed. Cystometry is performed as previously described in Visit #2 for the UUI subjects. The subjects will also have simulation of the procedure to be performed in the fMRI. Patients will have urine and vaginal swab samples collected and stored for possible future analysis (For example, urine may be analyzed for biomarkers and microbiome analysis). Future fMRI appointment is confirmed.

Visit 2: Urine pregnancy test performed (if patient is premenopausal and has not had hysterectomy or permanent sterilization procedure) and urine screen for UTI performed. FMRI procedures again explained to subjects. FMRI performed as described previously in visit 3 for fMRI UUI subjects. Subjects are given instructions and contact numbers to call in the event questions or problems arise. Subjects thanked and subject incentives given or arrangements made to give incentives.

Flow Diagram 1--- for UUI Subjects:

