Screening Visit (subject may also sign consent at this visit if desired): FMRI Study explained to subject. Subject administered OAB Awareness Tool and fMRI eligibility assessed. Subject given voiding diary instructions. Subject given copy of consent and either has visit scheduled to sign consent or if subject wishes, may sign consent at this time. If consent has been signed at this visit, the Past Medical History and Demographic forms will be administered at this time. Cystometry and fMRI procedures will be explained to the subject. Appointments for subject to undergo cystometry (see visit 1) & fMRI may be scheduled at this time or subject may be given research coordinator's info. for future contact. Arrangements made for patient to receive prophylactic antibiotics prior to bladder catheterizations.

Study Visit #1 Cystometrics: Subjects (up to 30-35) return for study visit with voiding diary and study eligibility (for FMRI as a normal control) confirmed. Consent signed if this has not happened previously and past medical history/Demographics sheet administered if consent signed at this visit. POP-Q exam performed if not performed in last year. Cystometry explained to subject. Urine pregnancy test and urine screen for UTI performed and have urine and vaginal swab samples collected and stored for future analysis. Cystometry and fMRI task performed. fMRI appointment confirmed.

Study Visit #2 fMRI: Urine screen for UTI and pregnancy test repeated. FMRI procedures again explained to subjects. FMRI performed. Subjects are given instructions and contact numbers to call in the event questions or problems arise. Subjects thanked and subject incentives given or arrangements made to give incentives.

4. Selection and Enrollment of Participants

4.1 Inclusion Criteria & 4.2 Exclusion Criteria:

All study participants must meet all the inclusion criteria as noted below to participate in the study. Additionally, if subjects have any of the exclusion criteria as specified below, they will be excluded from the respective portion of the study.

For the RCT:

Inclusion Criteria for the RCT: Women with Urgency Urinary Incontinence (UUI) who meet inclusion criteria and who choose to participate in the study will be enrolled. They must be able to understand the study procedures and agree to comply with them for the duration of the study. Inclusion criteria:

- Non-pregnant English-speaking women
- > 18 yo
- OAB Awareness scores ≥ 8

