Relevant background, management and modification of intervention or participant assessment for the above: Subjects will have bladder catheters placed for their cystometric evaluation and those who participate in the fMRI portion of the study will also be catheterized to undergo bladder filling for the fMRI task. Cystometric evaluation is considered a routine standard of care procedure for women with urgency urinary incontinence. The risks of bladder catheterization, although unlikely, include dysuria, hematuria and urinary tract infection. A recent meta-analysis concluded that prophylactic antibiotics for complex bladder testing decreased significant bactiuria with few side-effects, with a reported range of bactiuria of 1-8% in the groups treated with antibiotic prophylaxis.⁴⁶To decrease infection risks of bladder catheterization during this study, prophylactic antibiotics will be given to all subjects prior to and the day of catheterization. Nitrofurantoin or Trimethoprim/Sulfamethoxazole will be administered prior to and the day of catheterization. Subjects allergic to these medications will be given appropriate alternate antibiotic prophylaxis. Prior to the procedure, the patient will be informed regarding the procedure protocol and potential discomforts and side-effects. Participants will be clearly informed of their right to withdraw from the study at any time. Catheterization will be performed using sterile technique by nursing staff whose standard practice is to perform this procedure. Additionally, subjects will have urine dipsticks checked at study entry and prior to bladder catheterization to ensure absence of urinary tract infections. Subjects noting persistent urinary tract infection symptoms following the tasks will have urine dipstick testing and a urine culture performed. Subjects with evidence of a urinary tract infection will be treated. UTI, hematuria and dysuria occurrence will be tracked and AEs reported to the DSMB. If these events occur in 10% or more subjects, the protocol will be reviewed and revised.

FMRI

- Claustrophobia and Anxiety
- Dysuria, Hematuria and Urinary Tract Infection due to catheterization
- Unexpected Abnormality on MRI

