7.4 Reporting Procedures

Monitoring of Adverse Events & Frequency of Periodic Observations & Reporting & Follow-up: Adverse events will be monitored by spontaneous subject report and subject interviews and data review. At each clinic visit or follow-up telephone call, subjects will be asked to recall any adverse events since the time of their last contact (either via phone call, in-person clinic or study visit). The Study Coordinator (or her surrogate in her absence) will record the information using a standardized format and report the data to the PI's. If the AE is a reportable event as defined by the UNM HRPO (i.e. meets all the following criteria; it was unanticipated, caused harm or placed a person at increased risk of harm, and was more likely than not to have been related to the research) it will also be reported to the UNM HRPO (see UNM HRPO "Event form" attached which must be signed by the DSMB. The UNM HRPO will be notified of reportable events as soon as possible and within 5 days of the event date or

the "site awareness" date. AEs will be followed until they are resolved or considered stable, typically for one month, although this time will be extended to up to 4-6 months, depending on the instability of the event.

SAEs will be immediately (i.e. as soon as the Investigators or Study personnel are made aware that an SAE occurred) reported to the UNM IRB (HRPO) as per IRB guidelines and the NIH Project Officer and addressed by the DSMB if determined to be attributable to study participation (see SAEs below).

A Data Safety and Monitoring Board has been identified for this study. AE reports will be generated using standard forms, including the Adverse Event Case Report Form and Serious Adverse Event Case Report Form (see attached). The DSMB will meet quarterly for the first year and the DSMB will reassess and determine whether observations can be reviewed semi-annually thereafter. During the DSMP formal meetings the events will be reviewed. The severity of the event will be determined and an action plan to avoid recurrence of events (if found to be attributable to study participation) will be formulated and implemented. Research related adverse events will be reviewed and annual reports which include AE reports, subject enrollment/withdrawals and protocol violations will be generated for the University of New Mexico Health Sciences Center Human Research Protections Office (HRPO), Data Safety Monitoring Board and NCCAM/NCCAM Project Officer.

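### Normative controls have no scheduled contact after their fMRI catheterization, so later UTI, dysuria or hematuria reaches the 10% review trigger only by spontaneous report

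*Combined protocol and SAP*

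**What the plan says.** **Controls.** Section 3 (part B, normative controls) and Flow Diagram 2 give them two catheterizations: cystometry at Visit 1 and the fMRI bladder-filling task at Visit 2. Section 6.2.2 schedules the fMRI one week after cystometry, or within two. Section 3 ends Visit 2 with "Subjects are given instructions and contact numbers to call in the event questions or problems arise. Subjects thanked and subject incentives given", and Flow Diagram 2 finishes with "Subjects thanked and subject incentives given or arrangements made to give incentives". Nothing is scheduled after that.

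**Safety rule.** Section 7 (Bladder Catheterization) lists dysuria, hematuria and UTI as risks, says they will be tracked, and adds: "If these events occur in 10% or more subjects, the protocol will be reviewed and revised". Work-up depends on the woman coming forward: "Subjects noting persistent urinary tract infection symptoms following the tasks will have urine dipstick testing and a urine culture performed".

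**How events are found.** Section 7.4 says: "Adverse events will be monitored by spontaneous subject report and subject interviews and data review". The active part is: "At each clinic visit or follow-up telephone call, subjects will be asked to recall any adverse events since the time of their last contact".

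**Patients' repeat scan.** Section 3 describes Visit 12 as the follow-up fMRI, then says under Final visit 11/13: "Those who are in the subgroup who have undergone prior fMRI testing will have it performed at this session".

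**The concern.** Infection and irritation caused by a catheter would be expected in the days after it, so a question put at the catheterization visit cannot find them. For a control, the next occasion on which Section 7.4 would have her asked does not exist. Her events after the fMRI catheterization enter the tracked count only if she contacts the study herself.

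Two things are at stake. The 10% rule is the plan's only numerical safeguard against catheterization harm, and it would be applied to a count that is incomplete in one direction. In addition, controls have no UUI or OAB. The plan calls cystometry part of clinical care for patients, but controls are catheterized purely for research, so complete safety capture matters most for them.

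**Working it through.** **The plan's own figure.** The 10% trigger is a chosen threshold with no calculation behind it, so there is nothing to reproduce. If the denominator is all subjects (the plan does not define it), 10% of 152 + 30 = 182 is 18.2, and 10% of 152 + 35 = 187 is 18.7. Either way the trigger is 19 women.

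**Next scheduled adverse-event question after each control catheterization.**
- Cystometry (Visit 1): followed by Visit 2 after 1-2 weeks, with a urine screen. Covered.
- fMRI (Visit 2): no later visit or call in Section 3 or Flow Diagram 2. Table 1 follows the patient schedule (randomization, treatment, 6 and 12 months) and has no control column after the scan. Not covered.

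**Share of catheterizations.** Inputs: 152 patients, of whom up to 80 are scanned (cystometry plus two scans) and 72 are not (cystometry only), and 30-35 controls with two each.
- Total: 72×1 + 80×3 + 30×2 = 372, or with 35 controls 72 + 240 + 70 = 382.
- Without later contact: 30/372 = 8.1% to 35/382 = 9.2%. Within controls: 30/60 or 35/70, which is half.
- Section 3 lets unscanned patients with available urodynamic results skip cystometry. If all 72 did, the shares would be 30/300 = 10.0% to 35/310 = 11.3%.

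**Illustrative effect on the trigger.** Assumptions: events are independent with probability p per catheterization, and those after a control's second catheterization are reported with probability c. The only rate in the documents is 1-8%, for bacteriuria under prophylaxis, and it serves here as a stand-in for p. The documents give no value for c, so it runs from 0 to 1. The probability that a subject is counted is:
- unscanned patient: p
- scanned patient: 1 − (1−p)³
- control: 1 − (1−p)(1−cp)

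At p = 6% with 35 controls and c = 1, the expected count is 72×0.06 + 80×0.1694 + 35×0.1164 = 4.32 + 13.55 + 4.07 = 21.9, and 21.9/187 = 11.7%. With c = 0 the last term is 35×0.06 = 2.10, giving 20.0/187 = 10.7%.

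The chance of reaching 19 comes from convolving the three binomial distributions. Ranges cover 30 and 35 controls; only controls are affected.

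| p | c | Subjects counted | P(at least 19) |
|---|---|---|---|
| 4% | 1 | 7.9% | 0.13-0.16 |
| 4% | 0 | 7.2-7.3% | 0.07-0.08 |
| 6% | 1 | 11.7% | 0.74-0.78 |
| 6% | 0.5 | 11.2-11.3% | 0.68-0.71 |
| 6% | 0 | 10.7-10.8% | 0.60-0.63 |
| 8% | 1 | 15.4% | 0.98-0.99 |
| 8% | 0 | 14.1-14.2% | 0.95-0.96 |

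At p = 1% the chance is 0.000 whatever c is.

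**Controls alone at p = 6%.** Full capture: 1 − 0.94² = 11.6%. Half reported: 1 − 0.94×0.97 = 8.8%. None reported: 6.0%.

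**The case against.** The best defense is that the plan is not silent. Spontaneous reports and data review count under Section 7.4, controls leave with numbers to call, every catheterization has antibiotic prophylaxis and a prior dipstick, and women who note persistent symptoms are tested. This means c is probably above zero. It does not make c equal to 1, and data review adds little when no control data are planned after Visit 2. An incentive arranged for later may involve some contact, but the plan does not describe it as an adverse-event check.

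A second objection is that the Manual of Procedures and the data and safety monitoring plan, to which event capture is partly delegated, are not among the documents reviewed and may contain a post-procedure call. That stands as a limit. If such a call exists, the control pathway in Section 3 and Flow Diagram 2 should show it.

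Third, the pooled trigger is little changed when only controls are affected, and the rule itself is soft, with no stated denominator. This also stands.

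A reader might infer that scanned patients share the gap. The sentence placing their repeat scan in the final-visit session would make the next question the 6-month contact, 5-7 months after the sessions end. It would also raise the share to (30 + 80)/372 or (35 + 80)/382, about 30%. The documents do not support that as the plan. Section 3 itself defines a separate Visit 12 and numbers the scanned women's final visit 13. Flow Diagram 1, Section 6.2.2 (week 9) and Section 9.51 agree. Table 1 marks adverse events both at the week-9 scan and at the end-of-treatment visit. Section 6.2.5 allows scanned women three weeks rather than two for that visit. The stray sentence is a conflict to reconcile, not a demonstrated gap.

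**Conclusion.** The point holds for the 30-35 controls. After the second catheterization their UTI, dysuria and hematuria are captured only by spontaneous report, although the plan commits to tracking these events against a 10% trigger. This concerns about 8-9% of planned catheterizations and half of the controls' own.

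The direction of the error is certain, because unreported events can only lower the count. Its size is not in the documents. The illustration rests on a bacteriuria range used as a proxy, on independence between catheterizations, on an all-subjects denominator and on an unknown reporting fraction. Under those assumptions the effect on the pooled trigger is modest and the effect on the rate among controls is larger. It would be too strong to say that the trigger is disabled: at 8% it would very probably still be reached, and at 1% it would not be reached in any case.

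This is a worthwhile, inexpensive improvement in safety capture. It has no bearing on the efficacy comparison.

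**What to change.** Add to Flow Diagram 2 and Section 6 one scheduled call or message to each control about 1-2 weeks after the fMRI. It should ask directly about UTI, dysuria and hematuria, and events found this way should count toward the 10% trigger. The cost is one short contact for each of 30-35 women by staff who already make follow-up contacts. With the scan 1-2 weeks after Visit 1, the call falls at most about four weeks after Visit 1, which fits the month or less that the Précis gives for controls' involvement.

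Separately, reconcile the Final visit 11/13 sentence in Section 3 with the separate Visit 12 in Section 3, Flow Diagram 1, Table 1 and Sections 6.2.2 and 6.2.5, and make explicit that the end-of-treatment adverse-event check comes after the scan. Only if the repeat scan is in fact done at the final visit would scanned patients need the same call.

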 - Secondary objectives will be to compare group change in UUI episodes at 6 & 12 months, other voiding diary parameters (urinary frequency, pad counts, cure and "durable cure"), and change in the OAB-qSF and other questionnaires (see 1.2) at 2, 6 & 12 months.
- 2. Both a cross sectional study and RCT which will compare pre-treatment brain function in subjects with UUI to controls and compare the effect of hypnotherapy and pharmacotherapy on brain function in patients with UUI.
 - Up to eighty women (of the planned 152) with UUI will be recruited in order to obtain up to sixty analyzable fMRI datasets. Up to 30-35 normative controls will be recruited in order to achieve 25-30 analyzable fMRI datasets from normative controls. fMRI datasets from UUI patients will be compared to fMRI datasets from normative controls. The normative controls will be involved in the study for a month or less.
 - In addition, the same, up to 80, UUI subjects will also undergo fMRI analysis after receiving treatment (hypnotherapy or pharmacotherapy) for two months. Post treatment fMRI results from UUI subjects will be compared to their baseline images. These UUI subjects will complete the fMRI portion of the trial after being "on study" for 2 months but will continue to have follow up for the RCT analysis for one year (See #1 above)
 - Measured outcomes will be differences in baseline brain activation and connectivity in UUI subjects compared to controls as well as differences in treatment effect on brain activation and connectivity in subjects receiving pharmacotherapy compared to those receiving hypnotherapy

1. Study Objectives

1.1 Primary Objective:

- 1.1.1. To determine whether a mind/body therapy (hypnotherapy) is at least as effective and durable in treating urgency urinary incontinence (UUI) as a non-mind/body treatment (pharmacotherapy), comparing between group changes in UUI episodes recorded on voiding diaries at 2 months based on a non-inferiority design.
- 1.1.2. To determine whether hypnotherapy treatment of UUI (urgency urinary incontinence) is associated with greater modification of brain activation and connectivity on functional MRI than that which occurs following pharmacotherapy

1.2 Secondary Objectives:

- 1.2.1 To determine whether a mind/body therapy (hypnotherapy) is at least as effective and durable, in treating urgency urinary incontinence (UUI) as a non-mind/body treatment (pharmacotherapy).

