- \geq 3 UUI episodes/week for \geq 3 months

Exclusion Criteria for the RCT: Women who have any of the exclusion criteria as specified below will be excluded from study participation

- Women with a history of neurologic diseases such as Multiple Sclerosis, Parkinson's disease, stroke, or dementia
- History of schizophrenia or untreated bipolar disorder or current drug or alcohol dependence
- Women who have taken anticholinergic medications for UUI within the last 3 weeks (women who have taken anti-cholinergics for UUI but discontinued them > than 3 weeks ago may participate in the study) or have a sacral neuromodulator in place to treat UUI or have received Onabotulinum toxin A in the last 12 months to treat UUI
- Contraindications to anticholinergic medications (untreated narrow angle glaucoma, significant urinary retention or gastric retention)
- Pregnant women or lactating women, women who plan to become pregnant in the next year, or premenopausal women unwilling to use contraception if engaging in sexual relations during the year of study participation (hysterectomy is considered to be a form of contraception)
- Untreated urinary tract infection
- Prolapse which extends past the hymen (POP-Q points of ≥ 1+) which may be responsible for UUI symptoms
- Women who cannot keep the majority of the study therapy appointments or those without reliable contact phone numbers or methods of communication with the study personnel.

For the fMRI:

Inclusion Criteria for UUI subjects participating in the fMRI portion of the study: Women with UUI who meet criteria for the RCT and who are willing to participate in the fMRI portion of the study. They must be able to understand the study procedures and agree to comply with them.

Exclusion Criteria for UUI subjects participating in the fMRI portion of the study: Women who have any of the exclusion criteria as specified below will be excluded from participation in the fMRI portion of the study

• Women with a history of severe claustrophobia or ferro-magnetic implants such as cochlear implants, cardiac pacemakers or aneurysm clips.

Inclusion Criteria for normative controls participating in the fMRI study: These women must be able to understand the study procedures and agree to comply with them. Other criteria:

- Women 46-80 years old*
- Absence of UUI/OAB symptoms or treatment
- OAB Awareness Tools Scores <8
- Willingness to undergo fMRI

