*Explanation of age range for the above: In an attempt to assure comparable age ranges of controls to affected UUI subjects, we initially pooled data from both our pilot hypnotherapy and pilot fMRI studies and have found that the median patient age was 54 with the second quartile=46-54, and third quartile=55-62. We initially chose these quartiles as the age range for the normative control group but subsequently found that the age range was overly restrictive in the upper age ranges. We expanded the upper limit to 80 years in order to have flexibility in age adjustment of controls.

Exclusion Criteria for normative controls participating in the fMRI study: Women who have any of the exclusion criteria as specified below will be excluded from participation in the fMRI portion of the study

- Women with UUI/OAB
- Women with a history of neurologic diseases such as Multiple Sclerosis, Parkinson's disease, stroke, or dementia
- History of schizophrenia or untreated bipolar disorder or current drug or alcohol dependence
- Pregnant women or lactating women, women who plan to become pregnant in the next year, or premenopausal women unwilling to use contraception if engaging in sexual relations during the year of study participation (hysterectomy is considered to be a form of contraception)
- Untreated urinary tract infection
- Women with a history of severe claustrophobia or women with ferro-magnetic implants such as cochlear implants, cardiac pacemakers or aneurysm clips

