Statistical Analysis of 2.1 Normative controls vs. urgency incontinence subjects: Regions of interest containing the insula and anterior cingulate cortex will be analyzed in keeping with our a priori hypothesis using two way ANCOVA with group as the between subject's factor and age as a covariate. Pre-treatment β weights for both bladder filling and urgency regressor effect on anterior cingulate cortex and insula signal among normative subjects will be compared to the effect on signal in urgency incontinence subjects. The planned study size allows detection of differences between groups with an effect size >0.8 with power of 0.8, smaller than the observed effect size in our pilot study.⁴³ The effect size observed in our pilot study (Cohen's d ranged from 0.8 to 1.5) suggests that the study will be adequately powered (greater than 0.8) to reject the null hypothesis at an alpha=0.05. In addition to analysis of prior regions of interest, group wise whole brain contrast will also be performed using an identical statistical model. False positives will be corrected at a significance threshold corresponding to p <.005 applied in combination with a minimum cluster size threshold of 32 native voxels (p < 0.05), parameters derived from 10,000 Monte Carlo simulations.⁸⁰ Analysis of between group differences in functional connectivity will be performed in a similar fashion to that used to analyze brain activation evoked by bladder filling and emptying. The large observed effect size in our preliminary data (>3) suggests that the sample size used for proposed analysis of evoked potentials will be more than adequate.

Although the principal purpose of this analysis is to further explore the pathophysiologic underpinnings of UUI within the brain, we will also explore the use of evoked potentials and functional connectivity as a biomarker for UUI. Towards that end we will construct receiver operator curves (ROCs) based on fMRI output from controls and patients with UUI.

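### Controls start at age 46 but patients at over 18, so about a quarter of patients have no control of their age; the age-adjusted contrast and the ROC curves need an overlap-age check

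*Combined protocol and SAP*

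**What the plan says.** The inclusion criteria in section 4.1 admit as normative controls "Women 46-80 years old". For patients in the imaging part, the same section asks for "Women with UUI who meet criteria for the RCT and who are willing to participate in the fMRI portion of the study". The RCT criteria set age above 18 with no upper limit.

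The note explaining the control age range gives its purpose: "In an attempt to assure comparable age ranges of controls to affected UUI subjects". It reports from pooled pilot data that "the median patient age was 54 with the second quartile=46-54, and third quartile=55-62". Those two middle quartiles were the initial control range. The note then says: "We expanded the upper limit to 80 years in order to have flexibility in age adjustment of controls". The lower limit stayed at 46.

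For Hypothesis 2.1, sections 9.2 and 9.6 specify a "two way ANCOVA with group as the between subject's factor and age as a covariate". They state a detectable effect size above 0.8 with power 0.8 at alpha 0.05, and add exploratory ROC curves built from the same controls and patients. The Précis plans for "up to sixty analyzable fMRI datasets" from patients and 25-30 from controls. No section gives age matching, a restriction to overlapping ages, a group-by-age check, or any age adjustment of the ROC curves.

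**The concern.** The control range was meant to make ages comparable, but it was drawn from the middle half of the patient distribution and later widened only at the top. By construction, the youngest quarter of pilot patients lies below the youngest admissible control.

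A single age covariate bridges that gap by assumption. The model takes one straight age slope for both groups and carries the control signal down to ages at which no control was scanned. Patients under 46 help to estimate the slope, but the data cannot show whether it holds for controls of that age. The ROC curves are more exposed. Without age adjustment, a difference in age between the groups can contribute to the apparent discrimination.

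At stake are the patient-control comparison of Hypothesis 2.1 and the exploratory biomarker work built on it.

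**Working it through.** **Inputs.** Control ages 46-80, patient ages over 18, and pilot quartile limits of 46, 54 and 62 (section 4.1). Up to 60 patient and 25-30 control datasets (Précis). Detectable d of 0.8, power 0.8, alpha 0.05 (sections 9.2 and 9.6; two-sided assumed).

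**The plan's figure.** For a two-group t comparison, the noncentrality is d / sqrt(1/n1 + 1/n2) on n1 + n2 - 2 degrees of freedom. With 25 per group and d = 0.8, power is 0.79, so the stated figure corresponds to about 25 per group. With 60 patients and 25 or 30 controls, power at d = 0.8 is 0.91 or 0.94, and the detectable d is 0.675 or 0.633. The stated 0.8 is conservative.

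**Patients without a control of their age.** The first pilot quartile lies below 46: 0.25 × 60 = 15. The binomial 95% range is 9 to 22. For the upper end, assume normal ages with median 54 and SD = 8 / 0.6745 = 11.9. Then P(age > 80) = 0.014, or about 1 patient of 60. The pilot size is not given. If it were 20 to 60 patients (assumption), the standard error of the 25% would be sqrt(0.25 × 0.75 / n), or about 10 to 6 percentage points.

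**Mean age gap.** Under the same normal assumption, patients average about 54.

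| Controls (assumption) | Control mean age | Gap, all patients | Gap, patients 46-80 (mean 58.5) |
|---|---|---|---|
| Distributed like patients within 46-80 | 58.5 | 4.5 years | 0 |
| Spread evenly over 46-80 | 63 | 9 years | 4.5 years |

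An unadjusted ROC curve carries this gap directly.

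**Bias in the ANCOVA group term.** Set the true group difference to zero, give the signal a non-linear age effect, and fit group plus linear age in large samples weighted 60 patients to 27.5 controls. Results are in SD of the signal.

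| Age effect (assumption) | Controls distributed like patients | Controls spread evenly |
|---|---|---|
| Bend at 46: s × max(46 - age, 0)/10, s = 0.1 to 0.5 | 0.01 to 0.04 | below 0.01 |
| Smooth curve: k × ((age - 54)/10)², k = 0.1 to 0.2 | 0.07 to 0.13 | below 0.01 |
| Same curve, patients restricted to 46-80 | about 0 | -0.02 to -0.05 |

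Against d = 0.8, 0.04 is 5% and 0.13 is 16%. The bias scales with k (about 0.66 × k in the first column), so a stronger curve with k = 0.25 gives about 0.165, or 21%. The documents give no evidence of curvature of that size.

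**Power after restriction.** 60 - 15 = 45 patients.
- 45 vs 25: sqrt(1/45 + 1/25) = 0.249, detectable d = 0.709.
- 45 vs 30: sqrt(1/45 + 1/30) = 0.236, detectable d = 0.669.
- At the unfavourable end of the binomial range, 60 - 22 = 38 vs 25: detectable d = 0.733.

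All are below the stated 0.8. These are plain two-group figures; correlation between age and group would raise them somewhat.

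**The case against.** The investigators did consider age: they derived the range from pilot data, widened it to allow age adjustment, and put age in the model. Roughly three quarters of patients have controls of their own age. The count of 15 is soft, because it rests on a pilot of unstated size and imaging volunteers may differ from pilot patients. The comparison is listed as secondary in sections 3, 9.1 and 9.5.2 (although section 9.1 also calls its measures primary for Objective 2.1), and the ROC work is exploratory. The computed bias is small beside the pilot effect sizes of 0.8 to 1.5 for activation and above 3 for connectivity. All of this stands, and it limits the size of the point. It does not supply a control under 46, and no matching rule could.

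A reader might go further and infer that any non-linear age effect, or any difference in age slope between the groups, would appear as a false disease effect. The documents do not support that. The non-linear bias is modest under the cases tried. A different slope in patients and controls would be a real patient-control difference that varies with age, that is, effect modification; the single group term would then average over ages.

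A reader might also infer that the restricted comparison must replace the planned one. That does not follow either. Restriction removes the bias when controls are distributed like patients within 46-80, but slightly worsens it when controls are spread evenly, and it changes the population to which the result applies.

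**Conclusion.** The gap is real and follows from the plan's own criteria and pilot quartiles. About a quarter of imaging patients are expected to be younger than any control, and for them the adjusted Hypothesis 2.1 contrast rests on an assumed linear, common age slope. The likely effect on the ANCOVA group term is about 0.01 to 0.13 SD if controls are distributed like patients within 46-80, and smaller if they are spread evenly. These figures assume normal patient ages fitted to the pilot quartiles and illustrative age curves. The ROC curves are the weaker part, because no age adjustment is stated and the expected mean age gap is about 4.5 to 9 years.

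The point does not reach Aim 1 or the randomized Hypothesis 2.2 comparison, since neither uses the controls as its comparator. It warrants an added prespecified analysis; it does not invalidate the planned one.

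**What to change.** In section 9.6, and where section 9.2 repeats it:

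- Keep the all-age ANCOVA.
- Prespecify alongside it the same model in patients aged 46-80, and a test and estimate of the group-by-age interaction. Report both comparisons whatever they show. The interaction check is needed because restriction alone does not test for a differing slope.
- Build the ROC curves in patients aged 46-80 with age adjustment. Restriction alone could still leave a mean gap of up to about 4.5 years.
- Tabulate the age distributions of patients and controls, including the number of patients below 46 and above 80.

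The cost is SAP wording. About a quarter of patients leave the restricted analyses but remain in the trial, the randomized comparison and the all-age model. The detectable effect rises from 0.63-0.68 to 0.67-0.71, still better than the stated 0.8. Recruiting controls under 46 would close the gap more directly, but section 11.2 says that enrollment is complete, so the analysis is the practical place to act.
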